#### 4.1.2. Exclusion Criteria

Subjects are not eligible to participate in the study if they meet any of the following criteria:

- 1. A primary diagnosis of COPD or asthma as judged by the Investigator. Patients with comorbid COPD and/or asthma can be enrolled if bronchiectasis is their primary diagnosis.
- 2. Subjects receiving supplemental oxygen >12 hours per day.
- 3. Bronchiectasis due to cystic fibrosis.
- 4. Current smokers as defined per CDC: an adult who has smoked 100 cigarettes in his or her lifetime and who currently smokes cigarettes.
- 5. No evidence of bronchiectasis according to the BE-CT scoring system.
- 6. Known or suspected immunodeficiency disorder, including history of invasive opportunistic infections (eg, TB, histoplasmosis, listeriosis, coccidioidomycosis, pneumocystosis, aspergillosis) despite infection resolution, or otherwise recurrent infections of abnormal frequency, or prolonged infections suggesting an immunecompromised status, as judged by the Investigator.
- 7. Known history of HIV infection.
- 8. Established diagnosis of hepatitis B viral infection at the time of Screening, or positive for HBsAg at the time of Screening.
  - Subjects who have gained immunity for hepatitis B virus infection after vaccination (subjects who are HBsAg-negative, HBsAb-positive, and HBcAb-negative are eligible for the study).
  - Subjects with positive HBcAb are eligible for the study only if hepatitis B virus DNA level is undetectable.
- 9. Established diagnosis of HCV infection at the time of Screening. Subjects positive for hepatitis C antibody are eligible for the study only if HCV RNA is negative.
- 10. Currently being treated for NTM lung infection, allergic bronchopulmonary aspergillosis, or TB.
- 11. Active and current symptomatic infection by COVID-19.
- 12. Unable to perform technically acceptable spirometry that meet the ATS/ERS acceptability criteria with at least 3 acceptable flow-volume curves, at least 2 of which meet the ATS/ERS repeatability criteria for FEV1 during Screening.
- 13. Inability to follow the procedures of the study (eg, due to language problems or psychological disorders).
- 14. Receiving medications or therapy that are prohibited as concomitant medications (see Section 5.11.1 for prohibited concomitant medications).
- 15. Started oral or inhaled antibiotics as chronic treatment for NCFBE <3 months prior to the Screening Visit.

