#### 7.6. Chest CT Scan

At the Screening Visit, a chest CT scan image(s) for all subjects will be sent to the central reader for advanced centralized image analysis to evaluate if the NCFBE meets the enrollment criteria.

Only after this evaluation has been done and the CT scan has been read by the reviewers, can the subject be enrolled in the trial.

For each subject, the most recent chest CT (taken within 5 years of the Screening Visit) will be collected for centralized scoring by an independent Core Laboratory (LungAnalysis, Erasmus MC, The Netherlands). Before sending the chest CT scan, in DICOM format, to the central reading facility, the CT scan must be deidentified and coded by the study site. For those sites not familiar with deidentification instructions of chest CT scans, the central reading facility can consult and assist in the deidentification process.

For transfer of the deidentified chest CT scan, the central reading facility will use a Safe File Transfer Protocol. For secure large dataset transfer, SFTP file transfer will be used on web browser SURFfilesender services using data transfer vouchers. The options for secure transfer of the chest CT images will be described in the CT Scan Manual.

After transfer, LungAnalysis will perform a quality assessment of the CT scan(s). Next, the chest CT scan will be evaluated by a certified observer to confirm the diagnosis of bronchiectasis using the BE-CT scoring system. In case no or only minor bronchiectasis is identified using the BE-CT scoring system, the CT scan will be evaluated by a board-certified LungAnalysis chest radiologist on the presence or absence of bronchiectasis.

The screening for bronchiectasis will be determined using the BE-CT method. Each lobe will be assessed for presence and extent of bronchiectasis, as follows:

- 0=no bronchiectasis
- 1=bronchiectasis present in 0% to 32% of the lung lobe
- 2=bronchiectasis present in 33% to 66% of the lung lobe
- 3=bronchiectasis present in 67% to 100% of the lung lobe

The lingula will be assessed as the sixth lung lobe. Hence, the maximum BE-CT score is  $6 \times 3 = 18$ . In case of a BE-CT score of 3 or lower, a reassessment by a chest radiologist will be performed.

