# 10.4.6.5. Subgroup Analyses

Consistency of observed treatment effect on the rate of PEs will be explored across major subgroups as shown in the list below, if deemed appropriate.

- Age (12 to <18 years, 18 to <65 years,  $\ge$ 65 years; <75 years,  $\ge$ 75 years)
- Sex (Male, Female)
- Race (White, Asian, American Indian or Alaska Native, Black or African American, Native Hawaiian or Other Pacific Islander, Other)

- Ethnicity (Hispanic or Latino, Not Hispanic or Latino)
- Number of PEs in prior 12 months  $(1, 2, or \ge 3)$
- Chronic use of antibiotics at Baseline (Yes, No)
- Maintenance use of macrolides at Baseline (Yes, No)
- Pseudomonas aeruginosa colonization status at Baseline (Positive, Negative)
- Baseline BSI score ( $\leq 4$ , 5 to 8,  $\geq 9$ )
- Baseline BSI score (< median, ≥ median)
- Baseline CT scan score (< median, ≥ median)
- Baseline FEV1 % Predicted (<50%,  $\ge50\%$ )
- Geographical region (North America, Europe, Japan, the Rest of World).

Subgroup analysis will be based on a negative binomial model as used for the primary analysis. One model per subgroup will be fitted, omitting the fixed effect if it is identical to the subgroup. The ITT Analysis Set will be used. A summary for each level of subgroup presenting the same data as for the primary analysis will be produced. A forest plot of subgroups with rate of PEs and 95% CI displayed for each level of subgroup.

The main analysis for the primary and secondary endpoints will be repeated for the adolescent subgroup (12- <18 years of age), and separately for the adult subgroup for the On-Study estimand.

Additional subgroup analyses may also be performed if deemed appropriate.

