### 7.3. Demographic and Baseline Characteristics

Demographic and baseline characteristic variables will be summarized for all Analysis Sets as defined in Section 5. A summary by region will be provided, too. The summary will include:

Insmed Incorporated

- country,
- age,
- age group (12 to <18 years, 18 to <65 years, >= 65 years),
- age group >=18 years,
- age group (<75 years, >=75 years),
- sex,
- ethnicity,
- race,
- Baseline height,
- Baseline BMI,
- Baseline FEV1, pre- and post-bronchodilator (in L and % Predicted),
- Baseline FEV1 (% Predicted) < 50%,
- History of Chronic Obstructive Pulmonary Disease, identified through MedDRA coded terms (see Appendix K),
- History of Asthma, identified through MedDRA coded terms (see Appendix K),
- Hospitalized in prior 24 months for PE,
- CT Scan confirmation of Bronchiectasis,
- Use of Inhaled Steroids, identified through ATC coded terms (see Appendix K),
- Chronic use of Antibiotics,
- Bronchiectasis Severity Index (BSI) (see Appendix L),
- BSI categories (<=4, 5-8, >=9),
- Smoking status, including pack-years smoked (refer to Section 6.4.6 for calculation of pack-years smoked),
- Baseline eosinophil count (>=300/mm3, <300/mm3),
- Baseline QoL-B Respiratory Symptoms Domain Score (adults),
- Baseline BE-CT Score
- the stratification variables region (North America, Europe, Japan, and Rest of World), sputum sample (positive or negative for *Pseudomonas aeruginosa*) and the number of PEs in the previous 12 months (<3, >=3). Stratification variables will be presented as used for randomization.
- Geographic Region (South America, Eastern Europe, Western Countries, Asian Countries)

The distribution of participants randomized across region, country, and site will be presented for the ITT analysis set.

In addition, a listing will be produced for mismatches between randomized and actual strata.

CONFIDENTIAL Page 50 of 139

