### 8.2.6. Subgroup Analyses

Consistency of observed treatment effect on the Annualized Rate of PEs will be explored across major subgroups as shown in the list below.

- Age (12-<18, 18-<65 years,  $\ge$ 65 years); (<75 years,  $\ge$ 75 years); (>=18 years),
- Sex (Male, Female),
- All race groups (American Indian or Alaska Native, Asian, Black or African American, Native Hawaiian or Other Pacific Islander, White, Other)
- Ethnicity (Hispanic or Latino, Not Hispanic or Latino),
- Number of PEs in prior 12 months ( $<3, \ge 3$ ),
- Chronic use of Antibiotics at Baseline (Yes, No),
- Maintenance use of macrolides at Baseline (Yes, No),
- Pseudomonas aeruginosa colonization at Baseline (Positive, Negative),
- (Re-calculated) BSI score ( $\leq 4, 5-8, \geq 9$ ),
- Baseline BSI score (< Median, ≥ Median),
- BE-CT score ( $\leq$  Median,  $\geq$  Median),
- Baseline FEV1 % Predicted (<50%, ≥50%) post-bronchodilator,
- Stratification region (North America, Europe, Japan, the Rest of World),
- Geographical region (South America, Eastern Europe, Western Countries, Asian Countries, Oceania)
- Baseline eosinophil count (>=300/mm3, <300/mm3),
- Smoking status (Former smoker, Never smoked,),
- Use of inhaled steroids (Yes, No),
- History of Asthma, identified through MedDRA coded terms (see Appendix K) (Yes, No),
- History of Chronic Obstructive Pulmonary Disease, identified through MedDRA coded terms (see Appendix K) (Yes, No),

CONFIDENTIAL Page 56 of 139

• Hospitalized in prior 24 months for PE (Yes, No).

Subgroup analysis will be based on a similar negative binomial model as used for the primary analysis (see Section 8.2.1). The covariate of age group will not be included in models for subgroup analyses. One model per subgroup parameter will be fitted, omitting the fixed effect if it's identical to the subgroup or confounded with the subgroup. Crosstabulation of subgroup levels versus covariate levels via PROC FREQ will be utilized to identify any confounding. The ITT Analysis Set (see Section 5.2) will be used. A summary for each level of subgroup presenting the same data as for the primary analysis will be produced. A forest plot with annualized rate ratio of PEs and 95% CI will be displayed for each level of all subgroup parameters.

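### As printed, SAP 8.2.6 defines BE-CT subgroup levels that overlap at the median, unlike the protocol's CT-score split and the SAP's own BSI split

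*Protocol*

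**What the plan says.** Protocol 10.4.6.5 lists the subgroups in which consistency of the effect on the exacerbation rate will be explored. One is "Baseline CT scan score (< median, ≥ median": strictly below, and at or above.

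SAP 8.2.6 gives the corresponding entry as "BE-CT score ( $\leq$ Median, $\geq$ Median". Both signs include equality. The line directly above it reads "Baseline BSI score (< Median, ≥ Median", which is exclusive.

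On reporting, SAP 8.2.6 states: "A summary for each level of subgroup presenting the same data as for the primary analysis will be produced". It plans a single model for each subgroup variable and a forest plot showing every level. SAP 8.3.6 applies the same groupings to all secondary endpoints under the On-Study estimand.

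Protocol 7.6 describes the score. Each lobe is graded 0, 1, 2 or 3 (for example "1=bronchiectasis present in 0% to 32% of the lung lobe"), and "The lingula will be assessed as the sixth lung lobe". The stated maximum is 18. Exclusion criterion 5 in Protocol 4.1.2 is "No evidence of bronchiectasis according to the BE-CT scoring system".

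**The concern.** A median split should put each participant in one level. With both levels including equality, those exactly at the median qualify for both. On a finely graded measurement this would hardly matter. On a sum of six small integers, ties at the median are close to certain.

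If the rule were applied literally, the two rows could share participants and add up to more than the ITT Analysis Set. The subgroup display exists to show whether the effect looks alike in milder and more extensive bronchiectasis. Shared participants would draw the two rows together and make them look more alike than they are. Two adjacent median splits in one list would also follow different rules.

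**Working it through.** **1. Range of the score.** Six lobes times a maximum grade of 3 gives 6 × 3 = 18, which reproduces the maximum in Protocol 7.6. A participant with no bronchiectasis on BE-CT is excluded, so the lowest eligible score is 1 (one lobe graded 1). Eligible scores are whole numbers from 1 to 18.

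**2. Counts under each rule.** Let N be the number with a score and m the sample median.

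- Protocol rule: n(< m) + n(≥ m) = N.
- SAP rule as printed: n(≤ m) + n(≥ m) = N + n(= m).

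The excess is exactly the number at the median. It is zero only if the median falls between two integers.

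**3. How many that could be.** The documents give no BE-CT distribution, so the shapes below are assumptions. N is the planned 1,620 adults plus 40 adolescents, 1,660. Scores were rounded and held to 1–18, with 2,000 simulated samples per shape.

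| Assumed shape | Share at median | Number of 1,660 |
|---|---|---|
| Uniform, 1 to 18 | 5.6% | 93 |
| Normal, mean 7, SD 4 | 9.9% | 165 |
| Normal, mean 7, SD 3 | 13.3% | 220 |
| Normal, mean 9, SD 2 | 19.7% | 328 |

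The median fell between two integers in 1.7% of samples for the uniform shape and in none for the others.

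**4. Effect on the displayed contrast if levels are fitted separately.** Assume a share s at the median, the rest divided equally below and above, and an effect at the median halfway between the two sides. Set the effect to 0 below, 0.5 at and 1 above. Each row that includes the median holds (1 + s)/2 of participants.

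- SAP as printed: upper row 1/(1 + s), lower row s/(1 + s), contrast (1 − s)/(1 + s).
- Protocol split: upper row 1/(1 + s), lower row 0, contrast 1/(1 + s).

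As a fraction of the true below-versus-above difference:

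- s = 0.10: 0.90/1.10 = 0.82 as printed, against 1/1.10 = 0.91.
- s = 0.06: 0.94/1.06 = 0.89, against 1/1.06 = 0.94.
- s = 0.20: 0.80/1.20 = 0.67, against 1/1.20 = 0.83.

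The ratio of the two contrasts is 1 − s. The overlap therefore costs a further fraction s of the contrast beyond what the exclusive split already loses.

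**5. Effect if the subgroup is a model factor.** SAP 8.2.6 plans one model per subgroup variable but does not say whether levels are fitted separately or the subgroup enters as a factor. A two-level factor takes one value per participant. Someone at the median qualifies for two, so the rule could not be coded as printed and the programmer would have to choose a rule that the plan does not state.

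**The case against.** **The sign may be a reading error.** The point rests on one comparison sign in text extracted from a PDF, and that line came through in a different notation from the BSI line above it. Other signs look uncertain: the QTcF categories in SAP 9.10 leave exactly 500 msec unassigned, and Protocol Appendix 4 screens ALT with a strict sign although its own definition includes equality. This stands as a reason to check the source before editing. It does not show that the sign was misread.

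**The variable may differ.** The protocol says CT scan score and also describes BEST-CT and airway–artery scores. Those belong to a substudy of about 225 adults, whereas BE-CT is read for everyone at screening, and SAP 7.3 lists "Baseline BE-CT Score" among the baseline characteristics. Equating the two is a reasonable inference but remains one. The SAP's internal overlap stands without it.

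**Double counting is not certain.** A reader might infer that everyone at the median will be counted in both rows. The documents do not support that, because the way levels enter the model is not stated. What stands is that the printed levels overlap.

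**Little depends on it.** Both documents call these analyses exploratory, and neither plans an interaction test, so correlation between the rows invalidates no planned test. Part of the attenuation in the contrast also occurs under the protocol split. All of this stands and limits the point to the displays.

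**Silence in SAP Section 13 proves little.** A reader might infer an undisclosed change of method. Section 13 also omits the regrouping of prior exacerbations from 1, 2 or ≥3 in the protocol to <3 or ≥3 in the SAP. Its silence on the CT split fits a slip at least as well as a decision.

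**Conclusion.** The point holds as a defect in a stated analysis rule: the BE-CT levels in SAP 8.2.6, as printed, are not mutually exclusive, and they differ from both the adjacent BSI split and the protocol's CT-score split. Where the SAP means age groupings to overlap, it puts them in separate brackets; here the overlap is inside one bracket, which suggests a slip.

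The share of participants affected is unknown. About 6% to 20% is an illustration under assumed distributions, not an estimate for this trial. The loss of contrast also assumes separately fitted levels and an intermediate effect at the median. On those terms the pull toward apparent consistency is modest, and it is confined to exploratory tables and forest plots for the primary and secondary endpoints. A reader might infer that a trial conclusion is biased; the documents do not support this, because the multiplicity procedure, sample size and main analyses do not use these groupings. The point is minor and worth correcting because the correction is so small.

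**What to change.** Check the sign in the source PDF of the SAP. If it is as printed, change the BE-CT entry in SAP 8.2.6 to strictly below the median versus at or above it. SAP 8.3.6 inherits the correction. The levels then sum to the number of participants with a score and match the BSI line and Protocol 10.4.6.5. The cost is one symbol, with no effect on data collection, sample size or any confirmatory analysis. If the source already shows a strict sign, no change is needed.

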# 10.4.7. Safety Analysis

All safety data will be summarized by treatment received using descriptive statistics based on the Safety Analysis Set. All safety data will be listed for each subject as well.

# 10.4.7.1. Adverse Events

Adverse events will be coded using MedDRA. Treatment-emergent adverse events will be summarized by SOC and PT by treatment group. Non-emergent adverse events will be presented in the data listings.

The number and percentage of subjects with AEs will be presented by treatment and dose group.

The severity of AEs, the relationship to study drug, AEs causing study discontinuation, and SAEs will be similarly presented. All AEs reported during the study will be listed.

#### 10.4.7.2. Clinical Laboratory Tests

All clinical safety laboratory data (blood chemistry, hematology, and urinalysis) will be listed for each subject. Laboratory values outside the normal ranges will be flagged. If applicable, summary statistics (mean, range) for actual values and change from Baseline by treatment will be provided for each time point.

## **10.4.7.3.** Vital Signs

Vital signs will be listed and summarized including actual values and changes from Baseline.

#### 10.4.7.4. ECGs

Heart rate and corrected QT interval by Fridericia's formula will be derived from the dECG at each time point. The dECG data will be listed and summarized descriptively; outlier analyses for QTcF will also be performed.

## 10.4.8. Pharmacodynamic Analysis

The NE activity in sputum and blood will be calculated as percentage inhibition from the pretreatment activity. The pretreatment value is defined as the mean value of NE activities at Screening and Baseline and will be listed and summarized. All other biomarker levels at pre- and postdose levels will be listed and summarized.

Pharmacodynamic parameters that are planned to be analyzed are NE, CatG, PR3, and neutrophil functions including oxidative and bactericidal assays, neutrophil adhesion chemotaxis and others.

The results of NE, CatG, and PR3 activities, neutrophil functions, ANC, and other biomarkers will be listed by subject and time point. Note that ANC will be included in both safety and PD-related analyses.

The observed time to maximum inhibition and maximum inhibition for NE, CatG, and PR3 activities, neutrophil functions and ANC will be reported and listed for each subject. The NE activity in sputum and blood will be calculated as percent inhibition from the pretreatment activity. The pretreatment value is defined as the mean value of NE activities at Screening and Baseline and will be listed and summarized.

Descriptive statistics for NE, CatG, and PR3 activities, neutrophil functions, ANC, and derived activity parameters (maximum inhibition and time to maximum inhibition) will be presented by dose levels of brensocatib and placebo.

Individual figures of NE, CatG, and PR3 activities, neutrophil functions and ANC versus time will be presented with all subjects overlaid on the same plot for each dose level (spaghetti plots). Mean plots versus time will also be presented with all dose levels and pooled placebo overlaid on the same plot.

Plasma concentration data for brensocatib will be pooled with corresponding data from other studies for population PK/PD modeling of the exposure response relationship. The methods and results of any population PK/PD analyses will be described and reported separately.

## 10.4.9. Pharmacokinetic Analysis

For subjects participating in the PK/PD substudy and subjects with postdose PK samples in the main study, plasma concentrations of brensocatib will be listed and summarized by dose level over each scheduled sampling time using descriptive statistics (including arithmetic mean, SD, median, minimum and maximum, geometric mean, and percent coefficient of variation of the geometric mean, as appropriate). Individual plasma concentration data versus time for the PK/PD substudy will be presented in data listings, along with graphical plots of individual and geometric mean plasma concentration-time plots presented in linear and semi-logarithmic scale.

Actual sampling times and brensocatib plasma concentrations from sparse sampling will be listed but not summarized. The modeling output will be reported outside of the CSR.

Brensocatib plasma concentration data from this study will be pooled with data from other studies for the purposes of developing a population PK model. After an adequate structural model is identified, covariate analysis may be performed to evaluate the effect of intrinsic and extrinsic factors on the PK model parameters.

A detailed SAP for the population PK parameters and reporting will be developed. The PK SAP will be finalized and approved by signature prior to the database lock to preserve the integrity of the statistical analysis and study conclusions.

# 10.4.10. Population Pharmacokinetic Analysis

Plasma concentration data from this study will be utilized in population PK analysis as an exploratory measure. The individual PK parameters, such as  $C_{max}$ ,  $T_{max}$ ,  $AUC_{0-24}$ , elimination  $t_{1/2}$ , CL/F, and Vd/F, will be determined using a population PK model. PK covariates will be evaluated. The results will be reported separately.

## 10.4.11. Pharmacodynamic-Pharmacodynamic Analysis

Brensocatib PD data from this study will be pooled with data from other studies for the purposes of developing a population PK/PD model. Covariate analysis may be performed to evaluate the effect of intrinsic and extrinsic factors on the PD model parameters. A stand-alone modeling and simulation analysis plan will be written for the PK/PD and PD models. The modeling output will be reported outside of the CSR.

The relationship between brensocatib PD biomarkers of DPP1 inhibition (eg, NE, CatG, and PR3 levels and neutrophil functions) and outcome measures (ie, PE, FEV1, etc.) will be explored graphically. If appropriate, linear or nonlinear models may be used to further describe their relationship. In addition to the PD-PD analysis, other analysis methodologies, such as nonlinear mixed-effect modeling, may be employed to further characterize the PD/PD relationship of brensocatib.

